5.4.1. Liver Chemistry Stopping Criteria

As experience in humans is limited, it is standard GSK practice to collect information on liver events if they occur.

Liver chemistry stopping and increased monitoring criteria have been designed to assure subject safety and evaluate liver event etiology (in alignment with the FDA premarketing clinical liver safety guidance).

<http://www.fda.gov/downloads/Drugs/GuidanceComplianceRegulatoryInformation/Guidances/UCM174090.pdf>.

If liver chemistry abnormalities are seen (e.g., $ALT \geq 3 \times ULN$ and $bilirubin \geq 2 \times ULN$; $ALT \geq 5 \times ULN$; $ALT \geq 3 \times ULN$ if associated with symptoms believed to be related to hepatitis or hypersensitivity), it is recommended that the physician obtains follow-up liver chemistries until resolved, stabilized or returned to baseline.

It is recommended that additional follow-up assessments (e.g., viral hepatitis serology, serum creatine phosphokinase (CPK) and lactate dehydrogenase (LDH), liver imaging) are performed as clinically indicated to further evaluate other potential causes of the abnormalities and to assess the severity of the injury.

Refer to [Appendix 2](#) for liver safety required actions and follow-up assessments.

5.4.1.1. Study Treatment Restart or Rechallenge

Study treatment restart or rechallenge after liver chemistry stopping criteria are met by any subject participating in this study is not allowed.

5.5. Subject and Study Completion

A completed subject is one who has completed all study visits including the follow-up visit.

The end of the study is defined as the last subject's last visit.

5.6. Definition of an Analyzable Subject

A subject will be considered to be analyzable if they meet all of the following criteria:

1. Receive at least the Day 1 and Day 15 AVA doses,
2. Receive the raxibacumab dose, if randomized to that treatment, and
3. Complete the primary study endpoint assessment (anti-PA Ab concentration at Week 4).

Any subject who meets these criteria will be included in data analysis for the primary endpoint.

6. STUDY TREATMENT

6.1. Investigational Product and Other Study Treatment

The term 'study treatment' is used throughout the protocol to describe any combination of products received by the subject as per the protocol design. Study treatment may therefore refer to the individual study treatments or the combination of those study treatments.

Study Treatment ^a			
Product name:	GSK3068483 raxibacumab	BioThrax	Diphenhydramine
Formulation description:	Raxibacumab drug product comprises 50 mg/mL protein in 0.13 mg/mL citric acid, 2.8 mg/mL sodium citrate, 10 mg/mL sucrose, 18 mg/mL glycine, and 0.2 mg/mL polysorbate 80, pH 6.5 34 mL and 1700 mg deliverable per vial	BioThrax is made from cell-free filtrates of microaerophilic cultures of an avirulent, nonencapsulated strain of B. anthracis . The production cultures are grown in a chemically defined protein-free medium consisting of a mixture of amino acids, vitamins, inorganic salts, and sugars. The final product, prepared from the sterile filtrate culture fluid contains proteins, including the 83kDa protective antigen (PA) protein, released during the growth period and contains no dead or live bacteria. The final product is formulated to contain 1.2 mg/mL aluminum, added as aluminum hydroxide in 0.85% sodium chloride. The final product is formulated to contain 25 mcg/mL benzethonium chloride and 100 mcg/mL formaldehyde, added as preservatives.	Diphenhydramine route of administration (oral or IV) should be based on the temporal proximity to the start of raxibacumab infusion. For formulation information, refer to the labelling of the specific product chosen for administration
Dosage form:	sterile, liquid formulation in single-use vials	Sterile, milky-white suspension, in multi-use vials.	Refer to the labelling of the specific product chosen for administration
Unit dose strength(s)/ Dosage level(s):	40 mg/ kg	0.5 mL dose	Diphenhydramine should be administered at 25 – 50 mg. Refer to the labelling of the specific product chosen for administration for unit dose strength.
Route of Administration	IV	SC	Route of administration (oral or IV) should be based on the temporal proximity to the start of raxibacumab infusion.

Study Treatment ^a			
Product name:	GSK3068483 raxibacumab	BioThrax	Diphenhydramine
Dosing instructions:	For the combination treatment group, the raxibacumab dose will be administered just prior to the first AVA dose. The calculated raxibacumab dose to be administered to the subject will be diluted in normal saline with a final volume of 250 mL. The rate of raxibacumab infusion should be set for 15 mL/hour for the first 20 minutes and then adjusted to 125 mL/hour for the remainder of the infusion period. With this schedule, approximately 250 mL should be infused over the course of 2 hours and 15 minutes.	For the combination treatment group, the first BioThrax dose will be administered immediately after completion of the raxibacumab IV infusion, in the opposite arm. Refer to Section 2 of the BioThrax product label for dosing instructions. Key points to consider are: 
 • Shake the vial thoroughly; • inspect visually for particulate matter and discoloration prior to administration. Do not administer if present; • administer by SC route using a $\frac{5}{8}$-inch, 25- to 27-gauge sterile needle and syringe; • use a different injection site (e.g. alternating arms) for each sequential injection; 	For the combination treatment group, premedicate with diphenhydramine within 1 hour prior to raxibacumab infusion. Refer to the labelling of the specific product chosen for administration for dosing instructions
Physical description:	The drug product is filled into 50 mL USP Type I borosilicate glass vials, sealed with a 20 mm chlorobutyl rubber stopper and 20 mm flip-off aluminum seal, and stored at 2-8°C protected from light	BioThrax is supplied in 5 mL multidose vials containing ten 0.5 mL doses, and stored at 2-8°C (36° F to 46° F). Do not freeze.	Refer to the labelling of the specific product chosen for administration
Method for individualizing dosage:	Weight-based dosing.	None	None

a. Listed study products are commercially sourced

6.2. Treatment Assignment

Subjects will be assigned to Treatment Group 1 or Treatment Group 2 in accordance with a balanced independent randomization schedule generated prior to the start of the study. A corresponding set of randomization envelopes (one per subject) will be generated. A

randomization envelope for each subject will be opened prior to dosing (on day -1) to reveal the subject's treatment assignment. This process will ensure that study personnel and the volunteers will have no knowledge of the next treatment to be assigned.

Once a randomization number has been assigned to a subject, it will not be re-assigned to another subject. Randomization numbers will be assigned sequentially as subjects become eligible for dosing.

6.3. Blinding

This will be an open-label study. However, measures will be taken to reduce introduction of bias and the following will apply.

- Investigators, site staff and the subject have direct access to each subject's individual study treatment only with the opening of the randomization envelope.
- The following measures will be incorporated to blind specific aspects of the study in order to minimize bias and maintain study integrity:
 - Within the clinic, only the pharmacy will have access to the full randomization schedule.
 - The Sponsor team will be blinded except for the laboratory personnel, who must meet the following criteria:
 1. All analysts will be trained to Good Laboratory Practice (GLP) and follow Standard Operating Procedure (SOP) on the analysis of samples, inclusive of having Quality Control (QC) checks of all their work throughout the entire analysis.
 2. The final data will be peer-reviewed, minimizing the opportunity for any bias to affect the results. All samples will be analyzed and reported in a validated computer system with documented audit trails.
 - An external statistician and clinician (ie. not involved in conduct of the trial) will be responsible for performing the interim analyses, and will be instructed to only communicate to the team whether or not the futility boundary has been crossed, and will not share any subject-specific or summary-level information with the Sponsor team.
 - Monitoring will be completed by unblinded GSK monitors who will not share blinded information with the Sponsor team. An unblinded Clinical Research Associate independent from the study team will review monitoring reports and specific protocol deviations outlined in the Protocol Deviation Management Plan.
 - Throughout the course of study, the raxibacumab Safety Review Team (SRT) will evaluate accumulating aggregate blinded clinical trial safety data to monitor for potential treatment related effects (such as the identification of new safety issues, as well as the identification of clinically relevant changes in known safety issues).
 - GSK's Global Clinical Safety and Pharmacovigilance (GCSP) staff or delegates may unblind the treatment assignment for any subject with an SAE. If the SAE requires that an expedited regulatory report be sent to one or more regulatory agencies, a copy of the report, identifying the subject's treatment assignment, may be sent to investigators in accordance with local regulations and/or GSK policy.

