4.6. Benefit:Risk Assessment

Summaries of findings from both clinical and non-clinical studies conducted with raxibacumab (GSK3068483) can be found in the IB. Summaries of findings from both clinical and non-clinical studies conducted with AVA can be found in the prescribing information [[Anthrax Vaccine Adsorbed Package Insert, 2012](#)]. The following section outlines the risk assessment and mitigation strategy for this protocol

Clinical parameters will be monitored throughout the study in order to assess the safety and tolerability of AVA when administered alone or concomitantly with raxibacumab. The study design in place will allow in-stream blinded review of the aggregated safety and tolerability data during the study. Refer to protocol Section 7.1 for the timing of all clinical assessments.

Risk Assessment

Potential Risk of Clinical Significance	Summary of Data/Rationale for Risk	Mitigation Strategy
Study Drug		
Infusion Site Reactions (ISRs)	Infusion-related reactions were reported during administration of raxibacumab in clinical trials in healthy volunteers including reports of rash, urticaria, and pruritus.	Subjects will be premedicated with 25-50 mg of diphenhydramine up to 1 hour prior to the raxibacumab infusion, as recommended in the product label. Close monitoring of clinical parameters and adverse events will be conducted to assess effects of infusion site reactions.
Other		
Injection-site reactions	The most common ($\geq 10\%$) local (injection-site) adverse reactions observed in clinical studies with AVA were tenderness, pain, erythema, edema, and arm motion limitation.	Close monitoring of clinical parameters and adverse events will be conducted to assess effects of injection-site reactions.

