All available data from subjects receiving at least 1 dose of AVA will be included in the safety analyses if valid. Extra measurements (such as unscheduled or repeat assessments) will not be included in the by-visit summary, but will be included in subject listings. All adverse events and clinical laboratory outliers that occur following the first dose of study medication will be included in the presentations of adverse events and outlier episodes, including episodes that occur at unscheduled evaluations.

Study disposition will be presented for All Subjects Enrolled population as defined in Section 4.2.1. Demographics will be presented for Intent-to-Treat population as defined in Section 4.2.2. Immunogenicity summaries will be presented for all subjects in the Per Protocol population as defined in Section 4.2.3. Safety summary statistics will be presented for all subjects in the Safety population as defined in Section 4.2.4. Data from subjects excluded from an analysis population will be included in the data listings, but not in the summaries.

Baseline, defined as the last scheduled observation prior to dosing, will correspond to Day -1 for clinical laboratory evaluations and vital signs and to Day 1, prior to administration of any study drug, for anti-PA Ab levels and TNA titers. Additionally, for subjects randomized to Treatment Group 2, baseline will correspond to Day 1, prior to administration of any study drug, for anti-raxibacumab Ab levels. However, if a subject is missing the baseline collection, the previous non-missing evaluation will become the baseline value. If no baseline or previous to baseline evaluations exist then the baseline value will be treated as missing.

In general, data will be presented by treatment (i.e., “AVA” and “Raxibacumab + AVA”). Data for all study subjects combined will also be presented when appropriate.

Some minor modifications may be necessary to the planned design of tables, figures, and listings to accommodate data collected during the actual study conduct.

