4.9 Interim Analyses

Two interim analyses are scheduled to allow early termination of the study if a large effect of raxibacumab on AVA immunogenicity is confirmed at the interim. The first interim analysis will be performed after at least 30 analyzable subjects have reached the Week 4 endpoint. The trial is randomizing 34 patients to ensure that at least 30 subjects are analyzable, so it is possible that there will be more than 30 patients analyzed in the first interim. The second interim will be performed after the first 100 analyzable subjects have reached the Week 4 endpoint. There may also be additional subjects randomized to meet the total of 100 analyzable subjects for the second interim. The final number enrolled will be informed by the level of drop-outs observed in the first 34 subjects randomized.

These interim analyses will be performed on the per-protocol population by independent unblinded statistical and medical personnel using unblinded data.

For the interim analyses, the immunogenicity data will be summarized by the ratio of geometric mean concentrations (GMC) of anti-PA antibody levels with corresponding 95% CI. A two sample t-test for the log transformed data will be performed and a corresponding p-value will be provided which will be used to determine if the futility threshold has been crossed at the respective interim analyses. No imputations will be utilized for interim analyses. The study will be terminated early if the futility boundary is crossed at an interim, otherwise, recruitment for next phase will begin.

The futility thresholds for the interim analyses will be based on a rho (0.5) type II error spending function. The t-statistics for the boundaries, as calculated in East 5.4, are 1.0274 for interim 1 (sample size = 30 subjects), 0.4437 for interim 2 (sample size = 100 subjects) and -1.645 for the final analysis. These correspond to p-values for the t-test of p=0.848 at interim 1, p=0.671 at interim 2, and p=0.05 for the final analysis.

Note: The futility boundary will be recalculated by the unblinded statistician based on the actual number of subjects who comprise the primary analysis population for cohort 1. These boundaries will be calculated using East 6.2.

For these interim analyses, the results will include:

- calculations of futility boundaries (Table 14.2.3.1.1);
- a summary of statistical comparison of anti-PA antibody levels (Table 14.2.3.1.2);
- a demographic summary (Table 14.1.2);

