- a listing and a summary of the observed AEs (Listing 16.2.7.2, Table 14.3.1.2);
- a listing of serious AEs (Listing 14.3.2.2);

- a listing of AEs leading to withdrawal from study (Listing 14.3.2.3);
- a listing and a summary of laboratory assessments (Listing 16.2.8.1.1, Table 14.3.6.1, Table 14.3.6.2); and
- a listing and a summary of vital signs (Listing 16.2.8.2.1, Table 14.3.6.5, Table 14.3.6.6).

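### Interim reviewers receive unblinded safety outputs but have no documented route to pass on an imbalance seen mainly by arm, and the SAP opens the next cohort on futility alone.

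*Protocol*

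**What the plan says.** **What is produced.** SAP 4.9 lists, for each interim, a listing and summary of AEs, listings of SAEs and of AEs leading to withdrawal, and listings and summaries of laboratory data and vital signs. The work "will be performed on the per-protocol population by independent unblinded statistical and medical personnel using unblinded data". SAP 4.1 says data are in general presented by treatment.

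**What may be said.** Under Protocol 6.3 the external statistician and clinician "will be instructed to only communicate to the team whether or not the futility boundary has been crossed". The sponsor's team is to receive neither individual nor summarised data from them. No safety exception is given.

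**What happens next.** SAP 4.9: "The study will be terminated early if the futility boundary is crossed at an interim, otherwise, recruitment for next phase will begin". Protocol 4.3 is softer: later cohorts follow only if the discontinuation criteria are not met.

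**Who else looks at safety.** Protocol 4.6: "The study design in place will allow in-stream blinded review of the aggregated safety and tolerability data during the study". Protocol 6.3 assigns this to the Safety Review Team, on aggregate blinded data. It also lets sponsor pharmacovigilance staff unblind any subject with an SAE.

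**Which population.** SAP 4.9 places the interim analyses on the per-protocol population without separating safety from immunogenicity. SAP 4.1 says "Safety summary statistics will be presented for all subjects in the Safety population as defined in Section 4.2.4".

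**The concern.** Safety outputs at an interim are useful only if what they show can affect what follows. Here the external reviewers are the only people the plan has reviewing safety with the arms separated, and their one permitted message to the team concerns immunogenicity. The group charged with ongoing safety review sees both arms combined, where a moderate excess in one arm becomes a single diluted rate. At stake is whether Cohort 3, the bulk of the trial, could open while an arm difference is already visible to the external clinician and to nobody with authority to act on it.

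A smaller point concerns the population. The per-protocol set requires the Day 1 and Day 15 vaccine doses and a Week 4 result. If it also governs the interim safety summaries, those summaries leave out subjects who stopped early, including those who stopped because of an AE.

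**Working it through.** **1. The plan's own figures for the continuation rule.** Inputs (Protocol 9.2.1 and 9.3.2): SD 0.75 on the log10 scale, margin log10(1.5) = 0.176, looks at 30 and 100 of 534 subjects, futility boundaries 1.0274 and 0.4437. The statistic is Z = (difference in log10 means − 0.176) / (0.75 × √(4/n)). A simulation of 4,000,000 paths gives:

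| True ratio | Stop at interim 1 | Stop at interim 2 | Either | Table 5, either |
|---|---|---|---|---|
| 1 | 4.8% | 3.9% | 8.7% | 8.7% |
| 1.5 | 15.2% | 22.5% | 37.8% | 38.3% |

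The design figures reproduce. With futility as the SAP's only criterion, the rule opens Cohort 3 with probability 100 − 8.7 = 91.3% at ratio 1 and 100 − 38.3 = 61.7% at ratio 1.5 (Table 5), whatever the safety outputs show.

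**2. Routes by which safety information can reach someone able to act.**

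| Information | Documented route | Compared by arm? |
|---|---|---|
| Individual SAE | Sponsor within 24 hours (Protocol 7.4.1.1); may be unblinded (6.3) | Case by case |
| Related non-serious AE | Prompt notification (7.4.1.4) | No step stated |
| Pooled safety data | Safety Review Team (6.3) | No, blinded aggregate |
| Events at a site | Open-label investigator knows each subject's arm (6.3) | No study-wide comparison stated |
| Monitoring data | Unblinded monitors and an independent research associate (6.3) | Monitoring and deviations; no by-arm safety review stated |
| Interim safety outputs | External statistician and clinician (SAP 4.9) | Presumably yes, but no onward route stated |

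Only the last row is a by-arm review of all safety data, and it has no onward route.

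**3. What the by-arm view could show.** The documents give no AE rates, so these are assumed: 5% in Group 1 against a range in Group 2. At 1:1, 30 and 100 subjects give 15 and 50 per arm. Power is the sum of Bin(a; n, p2) × Bin(c; n, 0.05) over all tables with a > c and two-sided Fisher p < 0.05. The pooled rate is (5% + p2)/2.

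| Group 2 rate | Pooled rate | Power, 15 per arm | Power, 50 per arm |
|---|---|---|---|
| 10% | 7.5% | 0.6% | 6% |
| 15% | 10% | 3% | 24% |
| 20% | 12.5% | 8% | 51% |
| 25% | 15% | 17% | 75% |
| 30% | 17.5% | 27% | 90% |

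At 25% the reviewers at interim 2 would expect about 0.25 × 50 = 12.5 subjects against 0.05 × 50 = 2.5. The blinded team would see 15 in 100.

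**4. Exposure that follows.** Cohort 3 is at least 434 subjects. At 1:1, 434 / 2 = 217 would be infused.

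**5. Population.** AEs leading to withdrawal appear at the interim only as a listing, and SAP 4.1 keeps subjects excluded from a population in the listings. Those withdrawals would therefore not be lost. What remains open is the denominator of the AE, laboratory and vital-sign summaries: per-protocol under SAP 4.9, Safety under SAP 4.1 and 4.2.4.

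**The case against.** The strongest reply is that the trial is not short of safety routes. It is open-label at the site. SAEs reach the sponsor within 24 hours and can be unblinded, and related non-serious AEs are notified promptly. Protocol 6.6 brings the Medical Monitor into decisions on further vaccine after a hypersensitivity reaction. Protocol 10.5 lets the sponsor suspend the study at any time, with safety as a named reason. The limit in 6.3 concerns the team and the Sponsor team, so it is silent, rather than prohibitive, about a recipient outside them.

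All of this stands, and it rules out three stronger readings that a reader might infer:

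- *No safety signal can reach anyone able to act.* Not supported, for the reasons just given.
- *An excess of raxibacumab infusion reactions would be hidden.* Not supported. Only Group 2 is infused, so such events identify their arm even in pooled data. A pooled 15% at 1:1 would mean about 30% of those infused.
- *Cohort 3 opens automatically.* The SAP sentence reads that way, but Protocol 4.3 states a necessary condition, not a mandate, and 10.5 preserves the power to stop.

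The reply does not supply the missing link. The power to suspend needs information. Case-by-case SAE unblinding does not yield a by-arm comparison of non-serious events, laboratory values or vital signs. Silence about other recipients leaves the external clinician without an instruction on whom to tell.

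**Conclusion.** The concern holds in limited form. An imbalance visible mainly in the by-arm comparison has no documented route from the people who review it by arm to a decision-maker, and the SAP's continuation rule does not ask about safety. This should be corrected before the first interim. It is not a failure of safety oversight as a whole.

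The gap matters mainly at interim 2. Under the assumed rates of 5% against 20% or 25%, power is about 51% or 75% there, against 8% or 17% at interim 1. For gaps as small as 5% against 10% neither interim would show much. These figures only illustrate what the outputs could reveal; an experienced clinician would not apply a Fisher test as a rule.

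Two assumptions matter. First, the interim safety outputs are split by arm. This is inferred from SAP 4.1 and the use of unblinded data, since table shells are not in the text. Second, no charter or other document outside the protocol and SAP already sets an escalation route. The population point is an ambiguity to resolve, not a demonstrated loss of data.

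**What to change.** 1. In Protocol 6.3 and SAP 4.9, allow the external clinician one coded message separate from the futility result: either no safety concern, or safety concern, refer.
2. Name the recipient: a sponsor safety function outside the blinded team. Pharmacovigilance staff are the natural choice, but 6.3 now lets them unblind only subjects with an SAE. Their access would have to extend to the by-arm interim safety outputs after a referral.
3. In SAP 4.9, make recruitment of the next cohort subject to that message as well as to futility, and align the sentence with Protocol 4.3. What counts as a safety concern can be left to the external clinician's judgement or set out in a short charter.
4. State that interim safety summaries use the Safety population, as in SAP 4.1 and 4.2.4, and that the per-protocol population applies only to the immunogenicity comparison.

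The cost is wording. The external clinician and the outputs already exist, and sample size, alpha and futility boundaries do not change. The downside is that a referral, or a pause without a futility result, tells some sponsor staff that a safety question exists. It reveals no immunogenicity result.
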